6.4.2. Protocol Deviations

The investigator should not implement any deviation from or changes to the approved protocol. Additionally, the investigator should not implement any deviation from or changes to the approved protocol before such deviations/changes are reviewed and approved by the Institutional Review Board/Independent Ethics Committee (IRB/IEC) and regulatory authority per local regulation. Exceptions will be permitted in cases of immediate hazard to study participants or when the change involves only logistical or administrative aspects of the study (eg, changes in contact information). The investigator (or designee) should document and explain any deviation from the approved protocol.

6.5. Dose Modification

Dose modifications are not permitted.

6.6. Continued Access to IMP After the End of the Study

Participants who reach the EoTP visit (week 36) may be offered the option to roll over into a long-term, OLE study (ARGX-113-2010).

Participants will not be eligible to roll over into the OLE study if they discontinue from study ARGX-113-2009 (eg, withdrawal of consent). Participants who are eligible but choose not to roll over into the OLE study ARGX-113-2010 will complete a 7-week treatment-free follow-up period.

If a participant permanently withdraws from the study or is permanently withdrawn from the study by the investigator (Section 7.2), standard-of-care BP treatment may be administered by the participant's primary care physician.

6.7. Treatment of Overdose

For this study, a variation of more than 10% of the intended weekly amount of IMP will be considered an overdose.

An overdose is defined as a deliberate or accidental administration of IMP to a participant, at a dose greater than that assigned to that participant per the study protocol.

In the event of an overdose, the investigator should:

- Contact the medical monitor immediately.
- Evaluate the participant to determine, in consultation with the medical monitor, whether IMP should be interrupted or whether the dose should be reduced.
- Closely monitor the participant for any AE/SAE and laboratory abnormalities.
- Document the quantity of the excess dose and the duration of the overdose on the eCRF.

6.8. Concomitant Therapy

Participants must maintain a stable regimen of medications throughout the study. Any medication or vaccine (including over-the-counter or prescription medicines, recreational drugs, vitamins, and/or herbal supplements [including Chinese traditional medicine]) or other specific categories of interest that the participant is receiving at screening or receives during the study must be recorded on the eCRF along with:

- Reason for use
- Dates of administration, including start and end dates
- Dosage information including dose and frequency
- Brand name (for vaccines only)

All available vaccination history should be recorded as part of the participant's prior medication for vaccinations received in the past, or as concomitant medication for vaccinations received during the study, as described in the SoA (Table 1). Any vaccination information that the participant, or their caregiver can remember should be recorded on the eCRF (with the brand name of the vaccine and date of vaccination, if possible).

The medical monitor should be contacted if there are any questions regarding concomitant or prior therapy.

6.8.1. Concurrent Bullous Pemphigoid Therapy – Oral Prednisone

All participants, regardless of study IMP assignment, will also receive concurrent therapy with OCS, ie, prednisone at a starting dosage of 0.5 mg/kg/day at baseline (week 0), or an alternate OCS at an equivalent dose strength. The OCS dosage will be adjusted according to each participant's BP disease status throughout the study, with the goal of rapidly tapering systemic corticosteroid exposure and preventing and/or treating relapse. The oral prednisone dose adjustment procedure is described in Section 6.8.1.3.

If the investigator considers it necessary, oral prednisone ≤0.3 mg/kg/day (or equivalent OCS) may be administered to participants during the period between their screening and baseline visits.

6.8.1.1. General Oral Prednisone Information

Information on the formulation, unit dose strength, sourcing, packaging, and labeling of oral prednisone is summarized in Table 5.

Investigators, study site staff, and participants must comply with package labeling instructions for proper oral prednisone storage and handling.

During each on-site visit, study site staff will provide the participant with a supply of daily oral prednisone doses (or equivalent OCS) sufficient to last until the participant's next on-site visit. Participants will return any used and unused doses to the study site at their next on-site visit.

6.8.1.2. Oral Prednisone Dosing and Treatment Compliance

Participants will take oral prednisone (or equivalent OCS) daily at the dose directed by the investigator.

Participants will be provided a diary to record daily intake of each oral prednisone dose. The participant will bring their completed diary with them to every on-site visit so that staff can review the dosing record; during home visits, the participant will share their diary information with site staff.

If a participant misses one or more oral prednisone doses, they must contact the investigator. The missed doses must not be "made up"; rather, the participant will resume taking the daily oral prednisone dosage prescribed by the investigator, unless they have had a change in BP disease status that warrants dose adjustment (Section 6.8.1.3).

6.8.1.3. Oral Prednisone Dose Adjustment Regimen (Based on BP Disease Assessment)

Participants will receive IMP with concurrent OCS therapy. The recommended OCS dosing regimen is described below and displayed in Table 7.

The investigator should not deviate from the concurrent oral prednisone dosing regimen, except in matters where the safety of the participant may be compromised. After taking appropriate action to ensure the safety of the participants, such concerns should be documented and communicated to the sponsor's medical monitor and designee within 24 hours of the event.

For OCS doses not listed in Table 7, minimum and maximum recommended doses are provided. For participants with body weights of <45 kg or ≥110 kg, the investigator should propose OCS doses and inform the medical monitor to ensure consistency within the study.

Note: For the following list, "oral prednisone" refers to prednisone or an alternate OCS of equivalent dose strength.

- All participants will begin the study by taking oral prednisone 0.5 mg/kg/day starting at baseline (week 0; day 1).
- If the participant has not achieved CDA within 1-3 weeks of treatment with oral prednisone 0.5 mg/kg/day, then the dosage may be increased to 0.75 mg/kg/day for up to an additional 3 weeks. This period may be extended by 1 additional week (based on clinical judgment) to achieve CDA with an oral prednisone dosage of either 0.75 mg/kg/day or 1 mg/kg/day.

- A participant will be considered as a treatment failure if they do not achieve CDA after receiving the IMP with the prednisone dosing regimen described above. In case of treatment failure, IMP will be permanently discontinued (Section 7.1.1). Under these circumstances, the participant will be considered a nonresponder (Section 9.3.2).
- When CDA is achieved, the oral prednisone dosing regimen is adjusted as follows:
 - After CDA has been sustained for ≥2 weeks, the dose tapering schedule begins with the next lower oral prednisone dosage as listed in Table 7. Each new dosage must be maintained for at least 2 weeks provided that no new lesions (transient or nontransient) appear. Duration of tapering steps from escalated doses (>0.5 mg/kg/day) may be shortened based on clinical judgment.
 - For participants who achieved CDA on oral prednisone 0.5 mg/kg/day, the tapering steps are 0.3, 0.2, 0.15, and 0.1 mg/kg/day. For participants who required a dose increase to 0.75 or 1.0 mg/kg/day to achieve CDA, the oral prednisone dosage must first be tapered down to 0.5 mg/kg/day before proceeding to 0.3, 0.2, 0.15, and 0.1 mg/kg/day as shown in Table 7.
 - Further tapering below the level of minimal OCS therapy can be performed in steps of 2.5 mg/day until the participant is off oral prednisone therapy (Table 7). Each new dosage step must be maintained for at least 2 weeks, provided that no new lesions (transient or nontransient) appear.
 - If a participant has new lesions after the start of OCS tapering (ie, after CDA has been sustained for ≥2 weeks) but the investigator determines that it is not a relapse, prednisone tapering will be delayed. Under these circumstances, tapering can resume when no new lesions have appeared for at least 1 week (Table 7).
- If a participant relapses:
 - The oral prednisone dosage is increased based on the clinical judgment of the investigator, with the recommendation to return to the dose administered 2 tapering steps before the relapse. Tapering can be resumed after CDA has been sustained for at least 2 weeks on this increased dose.
 - If CDA is not achieved, the participant should resume the initial oral prednisone dosage of 0.5 mg/kg/day.
 - The participant must resume weekly on-site visits until CDA returns.

For concurrent oral methylprednisolone equivalent doses, refer to Table 16.

For home study visits that occur between mandatory on-site visits, the investigator will call the participant once weekly to review the participant's BP disease status and current oral prednisone (or equivalent) dosing regimen (Section 8.1.4).

Table 7: Concurrent Oral Prednisone Equivalent Doses (in mg) Based on Participant Body Weight

Table /.		Body weight category ^a													
Oral prednisone dose level	<45 kg	≥45 to <50 kg	≥50 to <55 kg	≥55 to <60 kg	≥60 to <65 kg	≥65 to <70 kg	≥70 to <75 kg	≥75 to <80 kg	≥80 to <85 kg	≥85 to <90 kg	≥90 to <95 kg	≥95 to <100 kg	≥100 to <105 kg	≥105 to <110 kg	≥110 kg
level	Minimum recommended daily OCS doses		Daily OCS doses ^b									Maximum recommended daily OCS doses			
mg/kg/day								mg/day	7						
1.0	40	45	50	55	60	65	70	75	80	85	90	95	100	105	110
0.75	30	30	35	40	45	45	50	55	60	60	65	70	75	75	80
Starting dose: 0.50	20	22.5	25	25	30	30	35	35	40	40	45	45	50	50	60
0.30	12.5	12.5	15	15	17.5	17.5	20	22.5	22.5	25	25	25	30	30	40
0.20	7.5	7.5	10	10	10	12.5	12.5	15	15	15	17.5	17.5	20	20	25
0.15	5	5	7.5	7.5	7.5	7.5	10	10	10	12.5	12.5	12.5	15	15	17.5
Minimal OCS therapy: ≤0.10	2.5	2.5	5	5	5	5	5	7.5	7.5	7.5	7.5	7.5	10	10	12.5
mg/day								mg/day	 						
7.5	NA	NA	NA	NA	NA	NA	NA	NA	NA	NA	NA	NA	7.5	7.5	7.5
5.0	NA	NA	NA	NA	NA	NA	NA	5	5	5	5	5	5	5	5
2.5	NA	NA	2.5	2.5	2.5	2.5	2.5	2.5	2.5	2.5	2.5	2.5	2.5	2.5	2.5
Off OCS therapy:	0	0	0	0	0	0	0	0	0	0	0	0	0	0	0

NA=not applicable; OCS=oral corticosteroids (oral prednisone or prednisone equivalent dose)

argenx

Notes: Each new dosage must be maintained for at least 2 weeks provided that no new lesions (transient or nontransient) appear. Duration of tapering steps from escalated doses (>0.5 mg/kg/day) may be shortened based on clinical judgment.

^a Body weight should be rounded to the nearest whole number.

^b The investigator should not deviate from the concurrent oral prednisone dosing regimen as specified in the table, except in matters where the safety of the participant may be compromised.

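### The post-relapse fallback to 0.5 mg/kg/day has no condition on the current dose, so read literally it lowers prednisone during uncontrolled relapse in a few previously escalated participants

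*Protocol*

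**What the plan says.** Protocol 6.8.1 describes OCS adjustment "with the goal of rapidly tapering systemic corticosteroid exposure and preventing and/or treating relapse". Section 6.8.1.3 then sets the regimen.

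- **Initial control.** Everyone starts at 0.5 mg/kg/day. Without CDA in 1 to 3 weeks, "then the dosage may be increased to 0.75 mg/kg/day for up to an additional 3 weeks", with one further optional week at 0.75 or 1.0.
- **Taper.** Participants who reached CDA on 0.5 go down through 0.3, 0.2, 0.15 and 0.1. Those who were escalated must first come back to 0.5. Below 0.1 the steps are 2.5 mg/day.
- **Relapse.** How far to raise the dose is left to the site physician's judgment, "with the recommendation to return to the dose administered 2 tapering steps before the relapse". The fallback follows: "If CDA is not achieved, the participant should resume the initial oral prednisone dosage of 0.5 mg/kg/day". The participant also returns to weekly on-site visits until CDA is back.
- **Adherence.** "The investigator should not deviate from the concurrent oral prednisone dosing regimen", except where safety may be compromised. Such concerns are to be documented and communicated to the medical monitor within 24 hours.

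The fallback is not limited to participants still below 0.5, and no period is given after which CDA counts as not achieved.

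**The concern.** A fallback for a relapse that has not responded should hold or raise the dose. Because the ladder extends above 0.5 for escalated participants, the recommended two-step return can place someone at 0.75 or 1.0 before the instruction to go to 0.5 applies. The stated response to an uncontrolled relapse is then a dose reduction, which runs against the aim in Section 6.8.1.

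OCS is the only other BP therapy allowed alongside IMP (Sections 4.2.4.1 and 6.8.2), so in the placebo arm it is the only active treatment. At stake are participant safety and consistency between sites that read the sentence differently.

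**Working it through.** **Inputs.** Ladders from Section 6.8.1.3 and Table 7 (mg/kg/day), by the highest dose needed for initial CDA:

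- Peak 0.5: 0.5, 0.3, 0.2, 0.15, 0.1, then 2.5 mg/day steps
- Peak 0.75: 0.75, then as above
- Peak 1.0: 1.0, 0.75, then as above

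**Rule.** Return dose = two steps above the dose at relapse. Change = 0.5 minus the return dose.

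| Peak | Relapse at | Return to | Fallback effect |
|---|---|---|---|
| any | 0.15 | 0.3 | +0.2, increase |
| any | 0.1 | 0.2 | +0.3, increase |
| any | 0.2 | 0.5 | 0, no change |
| 0.75 | 0.3 | 0.75 | −0.25, cut |
| 1.0 | 0.3 | 0.75 | −0.25, cut |
| 1.0 | 0.5 | 1.0 | −0.5, cut |

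Relapses below 0.1 also give an increase. At 70 to <75 kg, relapse at 0 mg/day returns to 5 mg/day and the fallback is 35 mg/day.

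Three further combinations have only one higher step, and the protocol does not say what to do there. If the return is assumed to stop at the participant's own peak, peak 0.5 with relapse at 0.3 gives no change. Peak 0.75 with relapse at 0.5, and peak 1.0 with relapse at 0.75, give cuts. The conclusion does not rely on these.

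**Size in mg/day, across the 15 Table 7 weight columns.**

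- 0.75 to 0.5: smallest 30 − 22.5 = 7.5 (45 to <50 kg); largest 75 − 50 = 25 (for example 100 to <105 kg). Relative cut 7.5/30 = 25% to 15/40 = 37.5%.
- 1.0 to 0.5: smallest 40 − 20 = 20 (<45 kg); largest 105 − 50 = 55 (105 to <110 kg). Relative cut 50/110 = 45% to 30/55 = 55%. The 20 mg/day and 45% ends come from the open-ended columns (<45 and ≥110 kg), where the investigator proposes the dose.
- China, Table 16, methylprednisolone: 24 − 18 = 6 to 60 − 40 = 20 mg/day; 32 − 16 = 16 to 84 − 40 = 44 mg/day.

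**Effect on NCOD in one affected participant.** Assuming nominal dose levels, 36 weeks on IMP and 3 weeks at 0.5 in place of the higher dose: 3 × 0.25/36 = 0.021 mg/kg/day, or 3 × 0.5/36 = 0.042 mg/kg/day, lower.

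**The case against.** The best counter-argument is context. The sentence sits under the relapse heading, directly after an instruction to increase the dose, and resuming the initial dose reads naturally as a step up for someone still below it. That is probably the intent. But an escalated participant has also already taken 0.5, so the wording fits a downward move too, and nothing in the text rules it out.

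The safety exception, the weekly visits and the investigator's discretion to stop IMP (Section 7.1.1) all stand and make real harm unlikely. Even so, holding the dose would rest on an exception that has to be documented and reported, for what is ordinary relapse care.

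The group is also narrow. Two of the three uncapped cuts need a 1.0 peak, reachable only through the optional extra week, and the two-step return is itself only a recommendation. This limits the size of the point but does not remove it.

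A reader might infer two further faults that the documents do not support:

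- **That the no-change cases are a defect.** A participant who relapses at 0.2 and returns to 0.5 is already at the fallback dose. The wording of the bullet allowing 0.75 is not confined to a first course.
- **That the fallback conflicts with treatment failure.** Section 4.1.3 and the SAP's Definition of Terms define failure as no CDA after 3 weeks at 0.75, without naming the course. But the failure bullet in 6.8.1.3 applies to participants "if they do not achieve CDA after receiving the IMP with the prednisone dosing regimen described above" and precedes the post-CDA and relapse bullets. Section 6.8.3 lists failure and two relapses as separate triggers, and Section 8.2.1.1 lists relapse and failure as separate statuses. These favour failure meaning initial control, in which case there is no conflict.

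**Conclusion.** The point holds as a narrow wording fault. For previously escalated participants on three rule paths (peak 0.75 or 1.0 with relapse at 0.3; peak 1.0 with relapse at 0.5), following the recommended return and then the literal fallback lowers prednisone by 7.5 to 25 or 20 to 55 mg/day while the relapse is uncontrolled. This assumes that the recommended two-step return is followed and that the fallback is read as unconditional, as written.

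The documents do not say how many participants would be affected. Few is a judgement, based on the need for prior escalation, an early relapse and failure to regain CDA. A reader might infer a threat to the treatment-effect estimate. The documents do not support that: the rule is the same in both blinded arms, and the NCOD shift is about 0.02 to 0.04 mg/kg/day in one affected participant. The case for correction is participant safety and site consistency.

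**What to change.** Replace the fallback bullet with wording such as:

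*If CDA is not regained on the increased dose and the current dose is below 0.5 mg/kg/day, increase to 0.5 mg/kg/day. A participant already at or above 0.5 mg/kg/day is not reduced solely because CDA is absent. Time above 0.5 mg/kg/day is limited as in the initial course (up to 3 weeks at 0.75, plus 1 optional week at 0.75 or 1.0), after which the investigator decides on IMP continuation under Section 7.1.1.*

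The time limit matters: an open-ended bar on reduction could keep someone at 1.0 well beyond the single optional week now allowed. Treatment failure should not be extended to relapse as part of this change, because that would add mandatory IMP stops. Stating whether Section 4.1.3 covers initial control only is a separate, optional clarification.

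**Cost.** A short amendment and a site communication, with no added visits, assessments or participants. The downside is slightly more steroid in a few participants. Against an immediate cut to 0.5, the most extra prednisone is 21 × 7.5 = 157.5 to 21 × 25 = 525 mg over 3 weeks at 0.75, and 28 × 7.5 = 210 to 28 × 25 = 700 mg over 4. If the optional week is at 1.0, it is 157.5 + 7 × 22.5 = 315 mg (45 to <50 kg) to 525 + 7 × 55 = 910 mg (105 to <110 kg).

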6.8.2. Prohibited Medications and Therapy During the Study

The following medications or treatments are not permitted while the participant receives IMP:

- Any systemic treatment for BP (except concurrent OCS), including but not limited to immunosuppressants, IVIg, SCIg, immunoadsorption, anti-CD20 biologics, tetracyclines with or without nicotinamide, dapsone, and IV or IM corticosteroids
- TCS (use must be discontinued before baseline)
- Any other biologic agent or experimental/study IMP
- Live or live-attenuated vaccines
- Complementary therapies, including traditional Chinese medicines, herbs, or procedures (eg, acupuncture), as assessed by the investigator

As discussed in Section 6.8.3, some of these treatments can be administered as rescue therapy if the participant discontinues IMP.

6.8.3. Rescue Therapy

Participants will discontinue IMP and may start rescue therapy if any of the following occur:

- The participant fails treatment with IMP (defined in Section 4.1.3)
- The participant relapses twice
- The participant presents with steroid toxicity (or any severe AE determined by the investigator to be related to OCS therapy)

Participants reporting any of the events mentioned above will permanently discontinue IMP (Section 7.1.1).

Rescue therapy may include OCS, TCS, conventional immunosuppressants (eg, azathioprine, cyclophosphamide, methotrexate, mycophenolate mofetil), tetracyclines with or without nicotinamide, dapsone, or IVIg. As described in Section 6.8.2, these treatments are permitted as rescue therapy following discontinuation of IMP.

7. IMP DISCONTINUATION AND PARTICIPANT DISCONTINUATION/WITHDRAWAL

Discontinuation of specific sites or the entire study is described in Appendix 1 (Section 10.1.11).

7.1. IMP Discontinuation

7.1.1. Permanent Discontinuation

Permanent discontinuation of IMP occurs when the participant stops receiving IMP before the end of the study, and does not resume receiving IMP. The participant also must not have withdrawn informed consent.

The investigator will document the primary reason for early discontinuation of IMP.

Participants who permanently discontinue IMP will be encouraged to remain in the study and attend mandatory on-site visits as specified in the SoA (Table 1). If the participant cannot attend these visits for any reason, the study site will perform an early study discontinuation (ESD) visit and safety follow-up visits as specified in the SoA (Table 1).

Unless consent from the study has been withdrawn, the participant will attend an early treatment discontinuation (ETD) visit. Study sites will attempt to perform the ETD visit within 7 days after the participant's final IMP administration. After the ETD, the participant will continue participation in the study through the rest of the 36-week treatment period and may receive rescue therapy (defined in Section 6.8.3). At week 36, the participant will complete the EoTP visit assessments (Table 1). If the participant meets rollover eligibility requirements (described in the ARGX-113-2010 protocol) at the end of the EoTP visit, they will be invited to immediately enroll in the OLE study ARGX-113-2010. If the participant does not meet rollover eligibility requirements or chooses not to enroll in the OLE study, they will participate in the 7-week treatment-free follow-up period. Refer to the SoA (Table 1) for data to be collected at the time of discontinuation of IMP and follow-up and for any other evaluations that need to be completed.

The following circumstances will result in the permanent discontinuation of IMP:

- Participant becomes pregnant or intends to become pregnant (refer to Section 8.4.6).
- Investigator decides that discontinuing IMP is in the participant's best interest (the sponsor will be informed).
- Participant develops an SAE or AE that contraindicates further administration of IMP in the investigator's opinion.
- Unblinding occurred.
- Participant exhibits any of the conditions outlined in Section 6.8.3. In these cases, participant may start rescue therapy.
- Any of the liver chemistry criteria resulting in temporary IMP discontinuation outlined in Section 7.1.2 is met, and the event is considered by the investigator to be related to the IMP.
- The participant develops any of the following, based on the sponsor's determination of relatedness:

- Any treatment-emergent adverse event (TEAE) of Common Terminology Criteria for Adverse Events (CTCAE) severity grade 4 that is considered related to IMP
- Any treatment-emergent SAE of grade 3 considered related to IMP
- Any infections of grade 3 or any serious infection considered related to IMP
- The participant develops any malignancy, either new or recurrent, other than basal cell carcinoma of the skin, regardless of relatedness.

